Only few studies focused on *neurobiological predictors* of treatment response. It is assumed that PTSD treatments mainly rely on extinction and memory re-consolidation processes (Careaga et al., 2016). Extinction, in short, is the attenuation or disappearance of a previously learned response when that response is not reinforced. The amygdala and ventral anterior cingulate cortex (ACC) are associated with extinction processes and there is evidence that these neurobiological correlates normalize with treatment ([name] et al., 2014). Non-responders of TF-CBT showed greater amygdala and greater right ventral ACC activation in response to masked fearful faces before treatment compared to responders (Bryant et al., 2008a, Dickie et al., 2011, Schmidt et al., 2013, Rooij et al., 2016). A smaller ventral ACC volume and a smaller hippocampus volume were associated with poorer treatment response to TF-CBT (Bryant et al., 2008b, Rooij et al., 2015a). During viewing of negative picture before treatment, both decreased (Bryant et al., 2008a) as well as increased activity in the dorsal ACC – a region associated with emotion regulation – was found to be predictive of PTSD treatment response (Rooij et al., 2016), and this inconsistency of findings might point to heterogeneity in PTSD populations. In addition, *non-responders* showed an increased demand on the executive frontostriatal network during a response inhibition task (Falconer et al., 2013, Rooij et al., 2016) and increased left inferior parietal lobe activation, a region associated with attention processes (Rooij et al., 2015b). In research into BPD response inhibition tasks are also used as a paradigm (see Van Zuthphen et al., 2015 for a review), but not yet for predicting treatment outcome.

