score of ≥ 2 in each of the three CPTSD symptoms clusters, plus functional impairment associated with these symptoms. A patient can only receive a PTSD or a CPTSD diagnosis, not both. The ITQ has demonstrated adequate internal reliability and validity (Cloitre et al., 2018; Hyland et al., 2017).

5.1.3 Biological predictors (see table 2):

- Biological parameters
 - Body measures: Weight, height, blood pressure
 - HPA axis (cortisol): Hair sample
 - Biomarkers: Fasting blood sample (BDNF, FKBP-5) & Full blood
- MRI session in subsample (60 min)
 - 3 Tesla-MRI (GE, VUmc): functional MRI with a face recognition , Structural MRI, Resting state MRI, DTI. In between scans a visual analogue scale (VAS) will be applied to assess distress during the scan session.

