⊗ Timing of the T2 measurement will be directly after trauma treatment, around 6 months

#The SCID-5-P at T0 is part of the regular intake procedure at the Sinai Centre

Table 2: Overview of add-on cognitive task, biological measurements, including MRI

MEASUREMENTS		DURATION	To	T1	T2	T3	T4	FU
in months			0	3	6 [⊗]	9*	12	18
COGNITIVE TASKS AT DAY 2		10 min						
Working memory	N-back	10	X*					
Interference	Stop/Signal task	15	X*					
PHYSICAL EXAMINATION AT DAY 2		30 min						
Body measures	Weight, height	10	X					
Blood pressure	Systolic and diastolic	5	X					
HPA axis (Hair)	Hair sample (cortisol)	5	X		X			
Biomarkers	Fasting blood sample (5HTTLPR, BDNF, FKBP5, oxytocin/OXTR) & Full blood	10	X		X			
MRI SESSION IN SUBSAMPLE WITHIN 2 WEEKS		60 min						

Functional MRI	Face recognition task	15	X		X			
Structural MRI		7	X		X			
Resting state MRI		10	X		X			
DTI		10	X		X			

DTI = Diffusion Tensor Imaging, MRI = Magnetic Resonance Imaging.

[&] Timing of the T2 measurement will be directly after trauma treatment, around 6 months

* Timing of the T3 measurement will be 3 months after T2, around 9 months

Table 3: Overview of duration of measurements (in minutes)

	To	T1	T2	T3	T4	Follow-up
Interviews	45	-	45	-	195	-
Questionnaires	91	15	88	15	88	27
n-back	10	-	-	-	-	-
TOTAL	141 (ca. 2.5 hrs)	15	128 (ca. 2 hrs)	15	278 (ca. 4,5 hrs)	27
Blood/hair	30	-	30	-	-	-
MRI	90	-	90	-	-	-
TOTAL for subgroup with MRI/blood/hair	261 (ca. 4 hrs)	15	218 (ca. 3,5 hrs)	15	278 (ca. 4,5 hrs)	27

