5.3 Study procedures

The study will lead to separate although integrated research projects for 3 PhDs.

A1: Is EMDR treatment more effective compared to integrated DBT-EMDR in patients with PTSD with comorbid BPD?

1. Systematic review and meta-analysis: do personality or dissociative symptoms predict effectiveness of PTSD treatment?
2. Do patients in the present study show higher response rate and effect sizes in integrated DBT-EMDR-treatment compared to EMDR-treatment alone after 12 months?
3. Is DBT-EMDR-treatment more effective as compared to EMDR-treatment alone in terms of PD symptoms, general psychiatric symptoms, disability, quality of life and health costs?
4. Do psychological (cognitive, affective, relational) factors predict (integrated DBT-) EMDRtreatment outcome?

A2: Is ImRs more effective compared to integrated SFT- ImRs in patients with PTSD with comorbid CPD?

1. Systematic review and meta-analysis: do personality or dissociative symptoms predict effectiveness of PTSD treatment?
2. Do patients in the present study show higher response rate and effect sizes in integrated SFT- ImRs -treatment compared to ImRs -treatment alone after 6-12-18 months?
3. Is SFT- ImRs -treatment more effective as compared to ImRs -treatment alone in terms of PD symptoms, general psychiatric symptoms, disability, quality of life and health costs?

4. Do psychological (cognitive, affective, relational) factors predict (integrated SFT-) ImRs treatment outcome?

B: Predictors of PTSD-treatment

1. Literature review: what is known on working mechanisms of PTSD treatment and do neurobiological findings predict PTSD treatment outcome?
2. Are PTSD treatments in this PTSD + PD population mainly working on increasing extinction of fear responses? Is this associated with decreasing salience, negative affect and cognitive control network activity and connectivity?
3. Do biomarkers (ACC volume, amygdala and ventral ACC and dorsal ACC activity, and/or hormonal/epigenetic factors (5-HTTLPR, BDNF, cortisol/FKBP5-methylation, oxytocin/OXTR) individually predict treatment outcome of PTSD treatment?

Timing of assessments

Baseline (To) visit

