Blood samples will be collected in 3 x 6ml tubes and the frozen samples will be stored at -80°C for intended future assaying of inflammatory markers (see Coelho et al., 2014), neuropeptides (such as oxytocin, 5HT), and epigenetics (such as FKBP5-methylation, OXTR- & 5HTTLPRgenes). The tubes will be stored without personal data linked to it, and they will only be marked with a subject number as described in section 9.1. below. Cortisol level (HPA-indicator) will be assessed in hair. This sample can be collected non-invasively by cutting a 1-cm distal to the scalp (1 month's exposure) sample of hair (Russell et al., 2012). All samples will be stored for 15 years (according to Archiefwet 1995).

In a subgroup: MRI session

Exclusion criteria for MRI research will be checked (metal implants, pregnancy, somatic disorders interfering with brain functioning, other (psycho-)pharmaca than at-least-3-months stabile dose SSRI or low-dose benzodiazepines, claustrophobia). A separate visit for MR scanning will be planned within 2 weeks of To, before the start of treatment, without causing a delay in treatment start. MRI sessions take at maximum 60 minutes (30-min functional MRI with a face recognition, and a suppression vs. reappraisal task, 5-min structural MRI, 8-min resting state MRI; and 8-min DTI) plus 30 min preparation. Next to patients, 40 healthy control persons, matched for age, gender, and education, will be asked to participate in one MRI session (no repeat MRI). These healthy control persons will be recruited via advertisements in local papers.

T1, T3 and FU

Patients do not have to come to the study center for T1, T3 and FU and can fill in the questionnaires via a login code at home if they have access to the internet (see Table 1.). Child trauma and life events questionnaires are only done at baseline (CTQ, LEC-5). Total duration of these measurements (T1, T3 and FU) will be between 15 and 30 minutes (see Table 3).

T2 visit

From all participants whose blood and hair was collected at baseline, blood and hair will be collected at T2 as well (duration 30 minutes). All participants who participated in the fMRI study at baseline will have their second MRI at T2. (duration 90 minutes). At T2, the CAPS-5 will also be conducted and participants will fill out the same questionnaires as at T0, except for the CTQ and LEC-5. Total duration of these measurements of will be ca. 2 hours (see Table 3).

Extra contact moment

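### Part B question 2 asks whether treatment works mainly through fear extinction, but no scheduled measure isolates extinction, and the patients-only change from T0 to T2 cannot show it

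*Combined protocol and SAP*

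**What the plan says.** Part B question 2 in section 5.3 has two parts. The first is the mechanism question: "Are PTSD treatments in this PTSD + PD population mainly working on increasing extinction of fear responses". The second asks "Is this associated with decreasing salience, negative affect and cognitive control network activity and connectivity", so falling network activity is put forward as a correlate of extinction, with extinction itself taken as established in some other way.

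The Introduction (Part B) defines the term: "Extinction, in short, is the attenuation or disappearance of a previously learned response when that response is not reinforced". It also says that "It is assumed that PTSD treatments mainly rely on extinction and memory re-consolidation processes", which names two processes, and it gives the only link to imaging: "The amygdala and ventral anterior cingulate cortex (ACC) are associated with extinction processes".

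The MRI content in section 5.1.3 is "functional MRI with a face recognition , Structural MRI, Resting state MRI, DTI", with a visual analogue distress rating between scans. Table 2 lists one functional task, the "Face recognition task", at T0 and T2. The MRI paragraph of section 5.3 adds a task contrasting suppression with reappraisal. Healthy controls "will be asked to participate in one MRI session (no repeat MRI").

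Section 7.1 uses controls for the baseline comparison only. The longitudinal fMRI analysis is in patients only, with time and condition as factors, and the connectivity analyses compare intervention groups and time points.

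**The concern.** Question 2 makes a claim about mechanism, and the word *mainly* makes it a strong one: extinction would have to be shown, and shown to outweigh the alternatives. If no measure captures extinction, the natural substitute is the change in brain activity between T0 and T2. That change has its own difficulty, because no group without trauma treatment is scanned twice. At stake is whether this imaging question can be answered from the data collected, and how a fall at the second scan may be interpreted. The treatment comparison on CAPS-5 is not at stake.

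**Working it through.** **1. Is extinction measured?** Sections 5.1 and 5.3 and Tables 1 and 2 contain no fear-conditioning task, no extinction learning or recall task, no trauma-cue challenge and no physiological fear index. The nearest items are:

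- Face task (T0, T2): reaches extinction only through the regional association stated in the Introduction. A region associated with extinction can change for other reasons.
- Suppression versus reappraisal task (section 5.3 text only, not in Table 2): concerns emotion regulation.
- Resting state, structural MRI and DTI (T0, T2): no learned response is elicited.
- Distress rating: general distress during the session.
- CAPS-5 (T0, T2, T4): PTSD symptom severity, whatever process reduced it.

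None of these separates extinction from re-consolidation, so none can support *mainly*.

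**2. Which contrasts are available?** The stated number of scan sessions in section 4.4 is 160. It reproduces as 80 patients at T0 + 40 controls at T0 + 40 patients at T2 = 160, which leaves no repeat scan for any control. Two longitudinal contrasts remain.

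- *Time effect in patients.* Everyone rescanned was assigned to EMDR or ImRs, alone or integrated. The effect of trauma treatment is therefore mixed with task and scanner familiarity, the passage of time and regression to the mean.
- *Time by condition.* A repeat-scan shift common to both conditions cancels. The contrast asks what adding DBT or SFT does, not whether trauma treatment increases extinction. Its precision is also limited: the detectable difference in change at 80% power, two-sided 5% (assumed; the protocol states no alpha), is (1.96 + 0.84) × √(2/n) SD of the change score. That is about 0.89 SD at 20 per condition and 0.63 SD at 40 per condition.

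**3. How easily could a bare time effect arise? (illustration)** Take a paired t-test, two-sided 5%, with no treatment effect and a repeat-scan shift of d within-person SDs. The noncentrality is d × √n. The values of d are assumed; the documents give none.

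| d | n = 40: noncentrality | n = 40: significant | n = 80: significant |
|---|---|---|---|
| 0.2 | 1.26 | 23% | 42% |
| 0.3 | 1.90 | 46% | 76% |
| 0.5 | 3.16 | 87% | 99% |

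The 40 is the number expected to return (section 4.4); 80 is the case in section 7.1 where all return.

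**4. Is network change already related to symptom change?** No such model appears in section 7.1. The mediation analysis covers hormonal and epigenetic factors only, and the machine-learning questions predict outcome or relapse.

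**5. What would such a model detect?** By Fisher's z, the correlation detectable with 80% power is tanh[(1.96 + 0.84)/√(n − 3)]. For n = 40 this is tanh(2.80/6.08) = tanh(0.46) ≈ 0.43. For n = 80 it is tanh(2.80/8.77) = tanh(0.32) ≈ 0.31.

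**The case against.** The strongest reply is that the plan never commits to the inference being criticised. Section 7 does not mention extinction and has no rule turning a fall in activity into an extinction claim. A reader might infer that such a fall would be reported as extinction, or that the same faces are shown twice. The documents support neither: they give the same task at both visits and do not describe the stimuli. What can be said is that a fall could not be told apart from the alternatives.

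Four further points stand at least in part:

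- It would be too broad to say that nothing related to fear is measured. CAPS-5 and the distress rating bear on it, and the Introduction links the amygdala and ventral ACC both to extinction and to responses to fearful faces. These remain proxies.
- It would be wrong to call the whole longitudinal analysis confounded. Time by condition is protected from repeat-scan effects common to both conditions, and familiarity with a face task does not apply to resting-state connectivity, where only general repeat-scan and time effects do.
- The missing extinction measure and the missing repeat control scans are separate problems. Rescanning controls would give a benchmark for repetition, but neither an extinction measure nor an untreated patient group.
- The mechanism question is in neither the objectives (section 2) nor hypotheses B (Introduction), which concern individual prediction. It is one item in a list of project questions, for an MRI subsample.

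The last point limits the weight of the matter. It does not make question 2 answerable.

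**Conclusion.** The point holds in limited form. As written, the first part of question 2 cannot be answered: no scheduled measure isolates extinction, and none separates it from re-consolidation. The patients-only time effect cannot fill the gap, because no group without trauma treatment is scanned twice. The time-by-condition contrast is sounder but answers a different question.

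The percentages in the working show only that modest repeat-scan shifts could produce a significant paired difference. A reader might take them as false-positive rates of this plan. They are not: the shifts are assumed, the test is one uncorrected paired t-test, and the plan uses SPM/FSL factorial models and permutation testing. Nor should the point be read as casting doubt on the primary CAPS-5 comparison or the prediction analyses, which do not depend on question 2. It is a modest and inexpensive correction to a secondary part of the project.

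**What to change.** In section 5.3, drop the extinction claim from question 2 and restate it, for example: *Is symptom improvement associated with T0–T2 change in salience, negative-affect and cognitive-control network activity and connectivity?*

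In section 7.1, add a model of T0–T2 CAPS-5 change on T0–T2 network change, adjusted for arm, alongside the planned time-by-condition analysis. State that the time main effect alone will not be interpreted as a treatment mechanism. In this model a uniform repeat-scan shift goes into the intercept and cannot create the association. A shift that varies between patients together with their symptom change is not removed, so the result remains an association.

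The cost is a change of wording and one extra model. CAPS-5 and MRI are already collected at T0 and T2, so no visits or scans are added. The price is a narrower claim and limited power: 80% only for a correlation of about 0.43 if 40 patients return, or about 0.31 if all 80 do (two-sided 5% assumed). That limit should be stated with the analysis.

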5.4 Withdrawal of individual subjects

Subjects can leave the study at any time for any reason if they wish to do so, without any consequences. The principal investigators can decide to withdraw a subject from the study for urgent medical reasons.

Reasons to terminate a patient's participation include:

- The patient withdraws her/his consent
- The nature of the patient's treatment is changed to coercive treatment (based on judicial ruling)
- The investigator considers a patient's continued participation in the study to be unjustifiable on medical or psychiatric grounds (i.e., because of side effects or unusual risks of the treatments).

If an individual patient is discontinued due to one of the above-mentioned reasons, this patient will be treated as usual in normal daily practice. The treating physician remains the primary caregiver during the study and will be contacted at the baseline visit and updated throughout the study. The treating physician will contact the study team in cases of important changes and will be responsible to apply for legal custody if appropriate.

All patients leaving the study early, regardless of the reason, will be requested to return to the site for an "early termination" visit to finalize participation. If the patient is not willing to complete all measures, priority will be given to the PCL-5 and OQ-45.

There are no consequences if a patient also refuses this.

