5.6 Follow-up of subjects withdrawn from treatment

Patients who drop-out out of (part of) the treatment remain in the study and will still be asked to complete the follow-up measures. Priority will be given to the online assessment with the PCL-5 and OQ-45.

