6.4 Follow-up of adverse events

All AEs will be followed until they have abated, or until a stable situation has been reached. Depending on the event, follow up may require additional tests or medical procedures as indicated, and/or referral to the general physician or a medical specialist. SAEs will be reported till the end of the study within the Netherlands, as defined in the protocol.

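### Section 5.4 ends study participation, not only treatment, when the investigator removes a patient for treatment side effects or risks, so the 12-month CAPS-5 may be missing for a harm-related reason

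*Combined protocol and SAP*

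**What the plan says.** Section 5.4 introduces its list with "Reasons to terminate a patient's participation include". One entry is the investigator's judgement that continuing is "unjustifiable on medical or psychiatric grounds (i.e., because of side effects or unusual risks of the treatments". The consequence is stated next: "If an individual patient is discontinued due to one of the above-mentioned reasons, this patient will be treated as usual in normal daily practice". Every early leaver, whatever the reason, "will be requested to return to the site for an 'early termination' visit to finalize participation". For that visit the section adds: "If the patient is not willing to complete all measures, priority will be given to the PCL-5 and OQ-45".

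Section 5.6 deals with the case where only therapy stops: "Patients who drop-out out of (part of) the treatment remain in the study and will still be asked to complete the follow-up measures". It too gives priority to the PCL-5 and OQ-45, completed online.

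Section 6.4 covers adverse events: "All AEs will be followed until they have abated, or until a stable situation has been reached". It adds: "SAEs will be reported till the end of the study within the Netherlands, as defined in the protocol". Neither sentence makes an exception for withdrawn patients.

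The primary model in section 7.1 uses the CAPS-5 severity score at T0, T2 and T4.

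**The concern.** In 5.4 a problem with the treatment leads to the end of data collection. A patient who leaves therapy stays under observation through 5.6. A patient whom the investigator takes out because therapy went badly does not. Missingness in the second group is tied to deterioration, the kind that a mixed model relying on observed scores handles least well.

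The situation is foreseeable. Section 6.2.2 describes suicidality and self-injury as very common in this population and says that starting a treatment such as EMDR or DBT can raise symptoms at first. Removals could differ by arm, because the PTSD-only treatments last 3-6 months and the integrated treatments 12 months (Summary), and neither patients nor therapists are blinded (5.2.2). The documents do not show which way any difference would go.

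Two things are at stake: the 12-month CAPS-5 comparison, and the per-group SAE and AE incidences in 7.3. The latter matter more here because the trial has no data safety monitoring board (6.5).

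**Working it through.** **Step 1. The three sections side by side.**

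| | Removed under 5.4 for side effects or risks of treatment | Dropped out of treatment, 5.6 |
|---|---|---|
| What ends | Study participation | Treatment, or part of it |
| CAPS-5 at T2 and T4 afterwards | Not provided for | Follow-up measures requested, with PCL-5 and OQ-45 first |
| Extra visit | One, at the time of leaving; may be refused | Not needed |
| Existing AEs | Followed to resolution or stability (6.4) | Same |
| SAE reporting | To study end (6.4) | Same |
| Self-injury questionnaire | Lapses with the regular assessments (6.2.2) | Continues where the patient agrees |
| New events between assessments | Therapists' weekly reports (6.2.2); not stated whether these continue | Same channel |

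**Step 2. What the primary model sees.** The CAPS-5 is scheduled at T0, T2 and T4 only (Table 1).
- Removal before T2 leaves the baseline score alone.
- Removal between T2 and T4 leaves T0 and T2.
- A CAPS-5 taken at the early-termination visit, if the patient agrees to it, is off schedule, and 7.1 gives it no place.

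The model gives valid estimates if missingness depends only on scores it contains. Worsening after the last scheduled CAPS-5 is outside it, and PCL-5 scores do not enter. Section 7 states no sensitivity analysis for missing data.

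**Step 3. The scale of the target difference.** Section 4.4 gives a difference of 0.5 SD, SD 20, within-person correlation 0.7 and 5 follow-up measurements, with 80% power. The target is therefore 0.5 × 20 = 10 points. Assuming two-sided alpha of 0.05, which the plan does not state:

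n = 2 × [20 × (1.960 + 0.842) / 10]² × (1 + 4 × 0.7) / 5 = 62.79 × 0.76 = 47.7, or 48 per condition.

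This is within 2 of the plan's 50, so 10 points is the right yardstick.

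**Step 4. Illustrative bias.** Let w be the fraction of an arm removed, and k the number of SDs by which their true T4 score is worse than the model predicts. Both are assumptions; the documents give neither.

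Bias in that arm's mean = w × k × 20.

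| w (patients of 63) | k = 0.5 | k = 1 |
|---|---|---|
| 2% (1.3) | 0.2 points, 2% of target | 0.4 points, 4% |
| 5% (3.2) | 0.5 points, 5% | 1.0 point, 10% |
| 10% (6.3) | 1.0 point, 10% | 2.0 points, 20% |

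**Step 5. From one arm to the contrast.** Bias in the difference = 20 × (w₁k₁ − w₂k₂). With equal removal and equal shortfall it is zero. With 10% against 5% removed, both at k = 1, it is 20 × (0.10 − 0.05) = 1.0 point. The table is therefore the contrast bias only if the other arm has no such removals.

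**The case against.** The best counter-argument is that the protocol already separates the two decisions. Section 5.6 is not limited to patients who leave by choice, so stopping therapy for side effects could fall there, leaving 5.4 for cases where study participation itself is unjustifiable. That is a sensible intention, but 5.4 does not express it: its parenthesis defines the grounds for ending participation by risks of the treatments, not of the assessments.

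A reader might infer that these patients also leave safety follow-up altogether, or that every month after removal is lost to safety observation. The documents do not support that. Section 6.4 follows existing events and reports SAEs to study end without excepting withdrawn patients. Section 5.4 also expects the treating physician to tell the study team of important changes, though whether this continues after removal is unstated. What remains open is the systematic capture of new events.

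Nor does the rule reach every harmed patient. Section 3 keeps patients who start medication or other treatment in an acute crisis in the study, and those who simply stop therapy fall under 5.6. The affected group is the subset the investigator removes, of unknown size.

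Three further objections stand. The early-termination visit seeks all measures first, so some symptom data close to the deterioration may be obtained. A CAPS-5 at T2 before removal would lessen the prediction error. And because 5.6 puts the PCL-5 and OQ-45 first, a bare reference to 5.6 would not secure the primary outcome.

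**Conclusion.** The point holds as a conflict of wording with a plausible effect on the primary outcome. As written, 5.4 ends data collection for a treatment reason where 5.6 continues it, and it provides no T2 or T4 CAPS-5 after removal. The resulting gap may be informative, and the model may fill it too favourably.

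The size is unknown. Under the assumed ranges (2-10% removed from one arm, scores 0.5-1 SD worse than predicted), that arm's mean shifts by about 0.2-2 points against a 10-point target. A reader might take the top of that range as a 10-20% bias in the treatment effect. That would need 5-10% removal in one arm, a full 1 SD shortfall, and no offsetting removals in the other arm; the documents support none of these.

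On safety, the finding is limited to new events: the scheduled self-injury questionnaire stops, and no section says who records later events in removed patients. This is an inexpensive improvement worth making, because missed T4 scores cannot be recovered later.

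**What to change.** Reconcile 5.4, 5.6 and 6.4:

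- In 5.4, separate the end of allocated treatment from the end of study participation.
- When the reason lies in the treatment, state that outcome assessment continues under 5.6, naming the CAPS-5 at T2 and T4 and the questionnaires at the other time points.
- State that SAE and self-injury collection continues for these patients, and who is responsible for it.
- Keep two exceptions: consent is withdrawn, or the assessments themselves are judged unjustifiable.
- Record and report the reason for removal by arm.

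The decision on when treatment stops is unchanged. The cost is protocol wording and a few more assessments from those already in Table 1, some of which patients will decline. The change therefore reduces the gap without closing it.
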